Prostate MRI is known to play an important role in prostate cancer detection and localization, and indeed prostate cancer staging[1]. It also aids in tumor detection when there is a biochemical suspicion of residual or recurrent disease after treatment[2],[3]. Compared to conventional prostate MR techniques from 5-10 years ago, which relied on morphology for tumor characterization, standard of care prostate MR in 2013 provides a wealth of information regarding tumor functionality[1]. mpMRI includes functional quantitative sequences such as Diffusion Weighted Imaging (DWI) and high temporal resolution Dynamic Contrast Enhanced (DCE) imaging. DWI is reflective of the random motion of water molecules at a cellular level, and is thus sensitive to cell membrane integrity, hypercellularity, enlargement of the nuclei and hyperchromatism. DWI (and more specifically, Apparent Diffusion Coefficient (ADC) derived from DWI) has been demonstrated on multiple occasions to correlate with Gleason score and serve as a biomarker for prostate tumor aggressiveness [4–9]. On DCE, prostate cancer shows early strong enhancement compared to surrounding normal prostate tissue. This enhancement pattern is thought to represent tumor angiogenesis and is necessary for further tumor growth[10],[11]. As a result, the number of vessels increases and these newly formed tumor vessels have higher permeability than do normal vessels because of weak integrity of the vessel wall. Studies have suggested that as the number of abnormal vessels in prostate cancer increases, the prognosis worsens[12][13]. Microvessel density in prostate cancer, an established independent predictor of pathologic stage, has been shown to correlate with DCE-MRI results[14].

b. EBRT and ADT for intermediate-high prostate cancer

In the era of PSA screening, many men are diagnosed with early-stage prostate cancer and have a good chance of cure. However, there are some patients, specifically those who present with unfavorable cancer based upon well-established features such as high prostate specific antigen (PSA), high Gleason score and/or those with advanced local disease (T-stage T2b or higher) who remain at high risk for prostate- cancer mortality. Androgen deprivation therapy (ADT) is very effective in controlling metastatic prostate cancer and improves survival when added to radiotherapy for localized disease. A significant gain in overall survival in those with locally advanced prostate cancer using a combination of external beam radiotherapy (EBRT) and ADT has been demonstrated by both the European Organization for Research and Treatment of Cancer (EORTC)[15] and the Radiation Therapy Oncology Group (RTOG)[16] and in others[17]. These randomized trials evaluated ADT given from six to thirty-six months. Long term (≥ 2 years) of ADT confers a modest survival benefit in men treated with radiotherapy for locally advanced prostate cancer compared with 6 months of ADT, but it is associated with increased toxic effects[18]. Therefore, identification of men in whom 6 months of ADT is sufficient for cure is important as is early identification of those who are not responding well to standard ADT.

i. Predicting those who will fail ADT therapy

Time to PSA failure and the rate at which PSA rises are surrogates for prostate cancer specific mortality (PCSM). Very recently[19], PSA nadir of ≤ 0.3 ng/ml after 2-3 months of neoadjuvant ADT (prior to initiation of EBRT) has been shown to be associated with improved long-term biochemical prostate tumor control, reduction in distant metastases, and prostate cancer-related death. This initial PSA response during ADT may reflect the sensitivity of the prostate tumor to androgen deprivation and in turn to the radio-sensitivity bestowed by ADT on the subsequently irradiated prostate tumor. Pre-EBRT PSA nadir may therefore represent a valuable early predictor for improved outcomes after radiation therapy for prostate cancer.

ii. Predicting those who will fail ADT/EBRT therapy

Looking further along the course of treatment with neoadjuvant ADT and 4 months of EBRT, D'Amico et al[20] used the Prentice criteria to assess whether measured lowest PSA concentrations (PSA nadir) or PSA immediately after treatment (PSA end) were early surrogates for prostate cancer-specific mortality, as both PSA end and nadir PSA are available before PSA failure. In this study they retrospectively reviewed 2 randomized controlled trials (cohort of 734 men), that showed improved overall and prostate cancer specific survival with radiotherapy and 6 months of androgen suppression compared with radio therapy alone. They found that men with PSA end values exceeding 0.5 ng/ml after EBRT and androgen suppression should be considered for long-term androgen suppression. Furthermore, an early endpoint such as PSA nadir after radiotherapy and at least 6 months of androgen suppression could identify men who are good candidates for future trials of additions of proven systemic therapies (i.e, one that extends survival in men with castration-resistant metastatic prostate cancer).

c. mpMRI as a biomarker for response to therapy in prostate cancer

A role for mpMRI as a non-invasive biomarker in assessing response to treatment options is currently an evolving area of great interest. In patients with low-risk prostate cancer on active surveillance, DWI

has been proposed to be a useful marker of prostate cancer progression and may help in identifying patients who may benefit from radical treatment [21],[22]. Recent studies have also investigated the use of mpMR to assess response to ADT[23] and radiotherapy[24],[25], with promising results.

After ADT, prostate gland shrinkage and fibrosis makes tumor difficult to detect on routine T2WIs. A feasibility study[23] evaluated the use of mpMR in monitoring response to ADT, and suggested that DCE as a marker of angiogenesis may help demonstrate ADT resistance, and DWI may help determine tumor cell death vs. residual tumor. In contrast to cytotoxic therapy, where ADC values increase (due to a lessening of the restriction of water molecules), ADT may not result in significant necrosis of prostate cancer cells, and in fact ADC values of prostate cancer post 3 months of ADT have been shown to remain the same[23]. In contrast, ADC values of areas where focal tumor was not suspected were significantly reduced with ADT, possibly due to acinar hypertrophy, fibrosis and basal cell hyperplasia.

Foltz et al. have looked at the very early post-radiotherapy changes in the prostate every 2 weeks up until 8 weeks of EBRT, and found that ADC was a possible candidate for early response to therapy, the optimal scan time being week 6 of EBRT[24]. Park et al have shown that ADC values in regions of tumor increased 1 and 3 weeks after initiating EBRT, and one month after completion of EBRT[25].

Specific to DCE, there is known to be an anti-angiogenic role for ADT in the prostate (androgen ablation has been shown to suppress glandular epithelial production of VEGF and induce apoptosis of endothelial cells). As PSA gene expression is down-regulated by ADT, PSA reduction post ADT may be secondary to androgen suppression rather than tumor cell death. It is therefore possible that DCE may act as a stronger surrogate for angiogenesis, rather than PSA.

There has been a pre-clinical study (on prostate xenograph models) evaluating a combination of parameters (ADC, DCE, tumor volume and PSA) which successfully predicted treatment response to a combination of ADT and radiotherapy, with a correlation coefficient of 0.85[26]. However, to our knowledge, no study has yet looked at a role for mpMRI in evaluating the effect of combined ADT and EBRT on prostate mpMR in humans. Nor has there been any work published on correlating PSA end with prostate mpMR, to determine if mpMR may act as an early biomarker in determining those who would benefit from long-term androgen suppression. We therefore propose to evaluate mpMR in response to combined therapy (ADT and EBRT), and to correlate quantitative mpMR parameters at early timepoints, with PSA end and PSA nadir.

II Specific Aims

1. The primary aim of this study is to explore the feasibility of mpMR as an early imaging biomarker to assess response of intermediate- and high-risk prostate cancer during treatment with neoadjuvant ADT.
2. A secondary aim is to explore the feasibility of mpMR as an imaging biomarker to assess response of bulky localized prostate cancer to combined ADT/EBRT.

3. To ascertain if the information provided using the non-ecoli 3 Tesla MRI images prior to starting EBRT can supplement CT information for Radiation Treatment (RT) planning purposes in men who are planning to undergo RT for prostate cancer.

III Study endpoints

1. The primary endpoint of this study is whether mpMR parameters measured after 2 months of neoadjuvant ADT therapy (TP1) correlate with nadir PSA post 8-weeks of ADT. In addition, we will determine whether mpMR parameters in areas of tumor (T) in those who fail neoadjuvant ADT (defined as PSA end ADT values $>.3$ ng/ml) are different to those who respond to ADT (defined as PSA end ADT $\leq.3$ ng/ml).
2. A secondary endpoint of this study is whether mpMR parameters measured after 6 weeks of EBRT (TP2) and 8 weeks after completion of EBRT (TP3) correlate with end PSA (defined as PSA level immediately after EBRT treatment). In addition, we will determine whether mpMR parameters in areas of T in those likely to fail combined ADT/EBRT (defined as PSA end values $>.5$ ng/ml) are different to those of responders (PSA end values $\leq.5$ ng/ml).

IV Subject selection

1. Inclusion criteria:
 - a. Adult males with unfavorable intermediate- to high-risk localized disease identified as one of the following three categories for unfavorable intermediatehigh risk factors, but must have visible disease on baseline MRI.
 - i. Clinical or radiographic T2b-T4 primary tumor
 - ii. Gleason score 7-10 in any core
 - iii. PSA ≥ 10 prior to initiation of therapy
 - b. Patients are deemed suitable for therapy with ADT and EBRT.
 - c. Subjects must be able to provide informed written consent prior to study entry.
2. Exclusion criteria:
 - a. The standard exclusion criteria for MRI exams will apply which include patients with pacemakers, non-compatible intra-cranial vascular clips, inner ear implants, and severe claustrophobia.
 - b. Patients who because of age, general medical or psychiatric condition, or physiologic status unrelated to the presence of prostate cancer are unlikely to be candidates for repeat MRIs, or cannot give valid informed consent.
 - c. Patients unwilling or unable to undergo the ecoli placement or multiparametric MRI exam.
 - d. Patients with a history of allergic reaction to latex or Gadolinium containing intravenous contrast agents.

- e. Individuals with renal disease or other contraindications to gadolinium will be excluded. The BWH standard MRI contrast screening criteria will be used to establish renal status.
- f. Patients who have had prior prostatectomy or prior androgen therapy.
- g. Patients with hip implant or any other metallic implant or device that results in significant distortion of the local magnetic field and compromise of the quality of the multiparametric MRI data.

V Subject recruitment/enrollment

Men with unfavorable intermediate-to high-risk prostate cancer are routinely seen at the multidisciplinary Lank Center for Genitourinary Oncology by a urologist, medical oncologist and radiation oncologist. The standard of care for this patient population is combination therapy consisting of complete androgen blockade and EBRT. Patients meeting eligibility criteria and choosing to have their ADT/EBRT care at Brigham and Women's Hospital will be recruited by the treating radiation oncologist, and asked if they wish to participate in the study. The study staff (PI and study coordinator) will obtain a list of new patients to be seen in GU radiation oncology clinic for prostate cancer. They will review the clinic note in EPIC to determine which treatment option for prostate cancer was decided upon, if the patient meets inclusion criteria for the study, and if the patient had a baseline MRI prior to starting treatment. If eligible for the study, the treating radiation oncologist/oncologist will be emailed by the study PI (see attached email template) to ask their permission to approach the patient to determine if the patient is interested in being part of the study, or the treating radiation oncologist can ask the patient directly if interested in being part of the study, and obtain consent.

[figure not shown]
To facilitate awareness of the study and to help with recruitment, we will post a flyer about the study in the physician and nursing radiation oncology clinical office for staff to see.

If the patient expresses interest in the study, they will be given a recruitment letter and a study consent form, which the radiation oncologist will review with them. Consent can be obtained at this time by the radiation oncologist. If so, the patient will be given a copy for their own record. However, there will be a second opportunity to consent the patient at the time of treatment planning for radiotherapy which occurs six weeks after the first LHRH injection. Patients who are consented at six weeks will already have undergone their baseline MRI and PSA, which is the standard of care for all intermediate- and high-risk prostate cancer patients. At this time, the radiation oncologist may review the study with the patient and obtain consent or the study radiologist may review the study with the patient and obtain consent. Either way, the physician who obtains consent will inform the study staff ([name] PhD and the study coordinator) of the patient's interest in the study. Those patients who elect to participate in the study will be contacted by the study coordinator to schedule the study MRIs and the serum PSAs, and to answer any remaining questions.

Any study patient may elect not to proceed with the study at any time.

VI Study Procedure

The timeline of the study is outlined below.

Baseline Standard of care prostate MRI and serum PSA will be obtained prior to starting ADT, as standard of care.

After an 8-week course of neoadjuvant ADT, serum PSA nadir and a prostate MRI will be obtained (**TP1**). EBRT will commence after an 8-week course of ADT for an 8-week period. However, 6 weeks into EBRT, subjects will undergo serum PSA level and a prostate MRI (**TP 2**). An end PSA at the end of EBRT will also be obtained. Six months after starting ADT, they will have a final prostate MRI and serum PSA level (**TP 3**). (*Please see section a, b, c, and d below for protocol on ADT, PSA, prostate MRI and EBRT respectively*).

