Zelevsky et al. report that 10-year relapse-free survival among patients with PSA nadir ≤ 0.3 was 74.3%, compared with 57.7% for patients with higher PSA nadir values ($P = 0.001$, $N = 1045$). In order to assess power for a test of whether mpMR parameters measured after 2 months neoadjuvant ADT therapy alone correlate with nadir PSA post 8-weeks of ADT therapy, we will make use of published data on the correlation between ADC change and nadir PSA. Foltz et al.[24] observed a correlation of 0.25 for nadir PSA with ADC percent change, between 6 weeks and the pre-RT baseline ($N = 10$). With 30 subjects, we anticipate 80% power to detect an absolute correlation of 0.49 or greater. Although this is greater than the correlation Foltz observed, we note that with a sample of size 10, using Fisher's transformation, an approximate 95% confidence interval for Foltz's estimate is (-0.45, 0.76), a wide interval which includes 0.49.

2. Within-Patient ADC Changes

Foltz et al.[24] reported a change in ADC between six weeks RT and baseline of -0.29 in tumor (2.8%, N = 36) and -0.56 in healthy tissue (N=10), with SDs of 0.23 and 0.18, respectively (in units of 10^{-3} mm²/s). Using the average variance above, we estimate a SD for ADC of 0.20. With N = 30 subjects, using this SD, we expect to have 80% power to detect a significant within-subject absolute difference in ADC between two time points of 0.14 or greater, based on a paired t-test at the 0.05 twotailed significance level, corrected for the 6 pairs of time points to be considered. This is much smaller than the difference of 0.81 observed in healthy tissue described by Barrett et al.[23], but larger than the very small difference of 0.03 that they observed in tumor. Foltz et al. observed changes in ADC between 4 weeks and baseline of 0.107 (B = 600) and 0.117 (B = 1200), both of which are less than 0.14.

3. Comparison of Normal Tissue ADC With Tumor

For comparisons between tumor and normal tissue, with 30 subjects we expect 80% power to detect an absolute difference in mean ADC of 0.19 or greater, based on a two-tailed two-sample t-test, adjusted for multiple comparison of time-points. Barrett's group observed a mean difference in ADC between tumor and healthy tissue of 0.20.

4. Comparison of ADC Changes between Patients who Fail Treatment and Those who do not.

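### Baseline PSA is collected for every man but enters no planned analysis, so the study cannot say whether MRI adds to the starting PSA; a supportive adjusted analysis would close the gap cheaply

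*Combined protocol and SAP*

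**What the plan says.** Section III.1 sets the primary question as "whether mpMR parameters measured after 2 months of neoadjuvant ADT therapy (TP1) correlate with nadir PSA post 8-weeks of ADT". It adds a comparison of tumour-area parameters between men whose PSA at the end of neoadjuvant ADT exceeds 0.3 ng/ml and those at or below it. Section III.2 does the same with TP2 and TP3 parameters, end PSA and a cut of 0.5 ng/ml.

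The 0.3 cut has a stated basis. Section I.b.i says that reaching it "has been shown to be associated with improved long-term biochemical prostate tumor control", and VII.1 reports "10-year relapse-free survival among patients with PSA nadir ≤ 0.3 was 74.3%, compared with 57.7" per cent for higher values.

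VII.1 plans the correlation around ADC change. It cites a published study that "observed a correlation of 0.25 for nadir PSA with ADC percent change, between 6 weeks and the pre-RT baseline" and states "With 30 subjects, we anticipate 80% power to detect an absolute correlation of 0.49 or greater".

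Baseline PSA is available throughout. Section VI says "Baseline Standard of care prostate MRI and serum PSA will be obtained prior to starting ADT", VI.2 repeats that PSA is checked before therapy, and section V notes that "Patients who are consented at six weeks will already have undergone their baseline MRI and PSA". Its only stated use is as one of three alternative eligibility criteria (IV.1.a). VII.1 to VII.5 cover a correlation, paired ADC changes, tumour against normal tissue, failures against non-failures, and descriptive rectal V70. None names baseline PSA, PSA change or any covariate.

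**The concern.** A man's PSA after eight weeks of ADT may depend partly on where it started. Because T stage or Gleason score alone can qualify a man, eligibility sets no floor or ceiling on starting PSA. If an MRI parameter is also related to starting PSA, it will correlate with 8-week PSA even when it says nothing further about what happened under treatment.

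The first specific aim is to explore MRI as a biomarker of response, and section IX hopes it may identify men who could benefit from longer androgen suppression. A reader of a positive result will ask whether the scan adds anything to a PSA value already in the chart. The data to address that will exist, but no planned analysis does so. Choosing the covariate and scale afterwards, with several MRI parameters and 30 men, would leave room to pick the more attractive version.

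**Working it through.** **Inputs from the documents.** N = 30, 80% power and an absolute correlation of 0.49 (VII.1). VII.1 states no significance level; two-sided 0.05 is assumed because it reproduces the figure.

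**The plan's own figure.** With Fisher's transformation, power = Φ(atanh(r)·√(n−3) − 1.96) = Φ(0.536 × √27 − 1.96) = 79.5% at r = 0.49. Detectable r = tanh(2.8016/√27) = 0.492. Simulating the t-test gives 81%. The stated figure reproduces.

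**Cost of one covariate.** Detectable partial r = tanh(2.8016/√26) = 0.500, and power at a partial r of 0.49 is 78.0%. The degree of freedom itself costs little.

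**Assumed inputs (not in the documents).** Let a be the correlation of MRI with log baseline PSA, R² the share of 8-week log-PSA variance explained by baseline, and b = √R². The three variables were simulated as trivariate normal, n = 30, at least 60,000 trials per setting, with t-tests on 28 df (simple) and 27 df (partial).

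*If MRI adds nothing beyond baseline PSA*, the true raw correlation is a·b, from 0.2 × √0.2 = 0.089 to 0.5 × √0.5 = 0.354. The raw test is then significant in:

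| a | R² 0.2 | R² 0.3 | R² 0.5 |
|---|---|---|---|
| 0.2 | 8% | 9% | 11% |
| 0.3 | 11% | 14% | 21% |
| 0.4 | 16% | 21% | 33% |
| 0.5 | 22% | 32% | 50% |

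If a or R² is zero the figure is 5%. The adjusted test stays at 5% when baseline PSA is error-free, and at 5 to 12% over this grid if its reliability is 0.7. For the 0.3 comparison, the unadjusted figures are 6 to 29% if a quarter of men exceed 0.3 and 7 to 33% if half do.

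*If the true raw correlation is 0.49*, partial r = (0.49 − a·b)/√((1−a²)(1−b²)). Example at a = 0.4, R² = 0.3: (0.49 − 0.219)/√(0.84 × 0.7) = 0.353. Adjusted power, against 81% unadjusted:

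| a | R² 0.2 | R² 0.3 | R² 0.5 |
|---|---|---|---|
| 0 | 89% | 94% | 99% |
| 0.2 | 72% | 74% | 82% |
| 0.3 | 63% | 61% | 62% |
| 0.4 | 54% | 48% | 40% |
| 0.5 | 46% | 36% | 22% |

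Expected 95% intervals: raw, tanh(atanh(0.49) ± 1.96/√27) = 0.16 to 0.72; partial 0.353, tanh(atanh(0.353) ± 1.96/√26) = −0.02 to 0.64.

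The adjusted 0.3 comparison is weaker. If a quarter of men exceed 0.3, power is 17-28% at a = 0.4 and 11-24% at a = 0.5, against 51% unadjusted. If half do, it is 21-34% and 12-29%, against 60%.

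**The case against.** The strongest reply is that the study asks a different question. It is an exploratory feasibility study of 30 men, its endpoint is whether MRI tracks 8-week PSA, and the raw correlation answers that. Added value over baseline PSA is not a stated endpoint. Nothing in the documents shows a problem either: they give neither a nor R², the background links ADC to Gleason score rather than PSA, and the ADC change behind VII.1 is already referenced to a baseline scan. Baseline PSA is also only one possible covariate. Finally, in the corner where the raw test misleads most (a = 0.5, R² = 0.5), the adjusted test has 22% power.

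Most of this stands. It rules out replacing the endpoint or letting an adjusted test carry the conclusion. It does not remove the gap: the data are already collected, and an interval beside the raw one shows the uncertainty instead of leaving it unexamined. Where MRI and baseline PSA are unrelated, adjustment gains power.

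A reader might infer that the table of 8 to 50% shows an inflated false-positive rate. It does not, because in those settings the raw correlation is truly non-zero (0.09 to 0.35), and detecting it is a correct answer to the stated question.

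**Conclusion.** The point holds as a cheap improvement. Baseline PSA is available for every man and enters no planned analysis, so a raw MRI-PSA correlation cannot be separated from whatever both share with the starting PSA. The size is unknown: the 8 to 50% range rests entirely on assumed values of a and R², normality on the log scale and a two-sided 5% level, and it falls to 5% if either a or R² is zero.

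Two stronger readings are tempting and unsupported. One is that absolute PSA and the 0.3 cut are the wrong target; the plan chose them deliberately and gives their prognostic basis. The other is that an adjusted result would settle whether the tumour responded. Section I.c itself cautions that a fall in PSA under ADT may come from androgen suppression and not cell death, so adjustment shows only what MRI adds to baseline PSA.

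**What to change.** Keep the primary endpoint, the 0.3 and 0.5 cuts, N and all MRI parameters unchanged. Then:

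- In VII.1, prespecify a supportive partial correlation or regression of log 8-week PSA on each MRI parameter, adjusted for log baseline PSA. Do this for the TP1 value named in III.1 and, separately, for the ADC change used in VII.1.
- Beside it, report the unadjusted estimate on the same log scale, so that only the adjustment differs, with 95% intervals for both.
- Fix one rule in advance for PSA values below the assay limit.
- Add the same covariate to supportive versions of the 0.3 comparison, the secondary end-PSA correlation and the 0.5 comparison.
- Make no significance claim from adjusted estimates. Describe them only as what MRI adds to baseline PSA, and state that a non-significant adjusted result is not evidence of no association.

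The cost is a few lines of text, some extra supportive estimates per MRI parameter, one degree of freedom in each adjusted analysis, and no new data. The primary analysis keeps its stated power. The adjusted estimates may be imprecise, as the power figures above show, and so should not carry the conclusion.

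### The 8-week ADT scan is never set against end PSA, and VII.4 powers the end-PSA split on a 3-month ADT change that no scheduled scan measures

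*Combined protocol and SAP*

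**What the plan says.** Section I.c closes its case for the study by proposing "to correlate quantitative mpMR parameters at early timepoints, with PSA end and PSA nadir". It presents end PSA as the marker for men who might benefit from long-term androgen suppression.

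Section III then assigns scans to PSA values. Endpoint 1 pairs TP1, the scan after 8 weeks of ADT, with nadir PSA. Endpoint 2 asks whether mpMR parameters "measured after 6 weeks of EBRT (TP2) and 8 weeks after completion of EBRT (TP3) correlate with end PSA", where end PSA is the value taken immediately after EBRT. A second sentence in endpoint 2 compares "mpMR parameters in areas of T in those likely to fail combined ADT/EBRT" (end PSA >0.5 ng/ml) with those of responders (≤0.5 ng/ml) and does not repeat which scan is meant.

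Aim 2 in Section II is to "explore the feasibility of mpMR as an imaging biomarker to assess response of bulky localized prostate cancer to combined ADT/EBRT". On the timing of TP3, Section VI says: "Six months after starting ADT, they will have a final prostate MRI and serum PSA level".

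Section VII.4 gives the power for the >0.5 split. It takes its SD from a published ADT study that measured change from before ADT to three months of ADT. It concludes that the trial can detect a change of about 15% over that same window.

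**The concern.** There are two separate matters.

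**The pairing.** Of the three follow-up scans, the 8-week ADT scan has the longest lead over end PSA, and it is the only one taken before EBRT. If the question is whether MRI can flag likely failures early, that scan is the most useful one to set against end PSA. Both measurements are already collected, but the comparison is not named.

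**The power statement.** VII.4 describes a change that the trial will not measure. The scheduled changes nearest to it are baseline to TP1 (ADT alone) and baseline to TP2 (ADT plus most of EBRT). The protocol itself describes different behaviour in those settings. Under ADT, "ADC values of prostate cancer post 3 months of ADT have been shown to remain the same"; under radiotherapy, "ADC values in regions of tumor increased 1 and 3 weeks after initiating EBRT". An SD from ADT alone may therefore not suit a scan taken during or after EBRT, and a reader cannot tell which analysis the stated power belongs to.

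**Working it through.** **1. Lead times.** Inputs are the dates on the sample MRI protocol schedule, with ADT start taken as the baseline date. That schedule numbers baseline as time point 1, so the text's TP1 appears there as Time Point 2. The text's labels are used here.

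| Event | Date | Day | Lead over end PSA | Paired with end PSA in Section III? |
|---|---|---|---|---|
| Baseline MRI | 1 Nov 2013 | 0 | +112 days | no |
| TP1 MRI | 27 Dec 2013 | 56 | +56 days | no |
| TP2 MRI | 7 Feb 2014 | 98 | +14 days | yes |
| End PSA | 21 Feb 2014 | 112 | – | – |
| TP3 MRI | 18 Apr 2014 | 168 | −56 days | yes |

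Baseline has a longer lead than TP1 but cannot show a treatment change, so TP1 leads among the follow-up scans only.

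Sensitivity: Section VI.4 gives 42 fractions, five per week. Starting on Monday 30 December with no missed days (assumed), EBRT ends on 25 February, and the leads become TP1 +60, TP2 +18 and TP3 −52 days. With TP3 at six calendar months (1 May) and end PSA on 21 February, TP3 is at −69 days. The order does not change.

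**2. VII.4's window.** Three months from 1 November is 1 February, day 92.
- From TP1: 92 − 56 = 36 days later.
- To TP2: 98 − 92 = 6 days earlier.
- Fractions given by day 92: 5 weeks × 5 = 25 of 42 (60%).
- Fractions given by TP2: 6 × 5 = 30 of 42 (71%).
- Fractions given by TP1: none.

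If three holidays are skipped (assumed), the counts are 23 and 28. Either way, no scan follows three months of ADT alone.

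**3. VII.4's detectable difference.** The plan's arithmetic reproduces: 0.227/√(0.25² + 0.75²) = 0.287, and 0.51 × 0.287 = 0.146, given as 0.15. The 0.51 itself does not reproduce for two groups. VII.4 states no alpha, so two-sided 0.05 is taken from VII.2.
- 8 versus 22, normal approximation: (1.960 + 0.842) × √(1/8 + 1/22) = 2.802 × 0.413 = 1.16 SD.
- 8 versus 22, noncentral t with 28 df: 1.20 SD.
- One-sided 0.05: 1.05 SD, still about twice 0.51.
- One-sample formula with N = 30: 2.802/√30 = 0.511 SD, which matches the stated value.

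Power at 0.51 SD with 8 versus 22 is Φ(0.51/0.413 − 1.960) = Φ(−0.72) ≈ 23%, or 22% by noncentral t. In ADC units, 1.20 SD is 0.34 × 10⁻³ mm²/s at SD 0.287 (34% of the 1.006 baseline) and 0.27 at the unadjusted SD 0.227.

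**4. What an added TP1 correlation could show.** By Fisher's z with N = 30, the detectable |r| at 80% power is tanh(2.802/√27) = 0.49, which reproduces VII.1. The 95% CI, tanh(atanh r ± 1.96/√27), is 0.16 to 0.72 if r = 0.49 and −0.12 to 0.56 if r = 0.25.

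**5. Cost in false positives, per parameter, unadjusted, independence assumed.**
- Correlations only: two tests give 1 − 0.95² = 9.8%; three give 1 − 0.95³ = 14.3%.
- Five tests: 1 − 0.95⁵ = 22.6%.
- Correlation and split at TP2 and TP3 (four tests): 1 − 0.95⁴ = 18.5%. With TP1 added to both (six tests): 1 − 0.95⁶ = 26.5%.

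**The case against.** The best defence is that Section III follows the aims. Aim 1 concerns neoadjuvant ADT and takes the pre-EBRT scan. Aim 2 concerns combined therapy and takes the scans during and after EBRT. TP1 precedes all EBRT, so it cannot measure response to the combination. The proposal in Section I.c can be read as TP1 with nadir PSA and TP2 with end PSA. TP2 is a defensible early scan, since Section I.c cites a study with "the optimal scan time being week 6 of EBRT". All of this stands, so a reader who infers that leaving out TP1 is an error or a contradiction goes further than the documents allow.

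A reader might also infer that the >0.5 split has no defined scan and could be run on any of them. The sentence adds to endpoint 2 directly after TP2 and TP3 are named, and endpoint 1 has the same structure with TP1. In context TP2 and TP3 carry over; what is missing is an explicit statement.

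Nor is the TP3 pairing invalid. Endpoint 2 speaks of correlation, and aim 2 of assessing response. TP3 can serve that purpose but cannot predict a PSA measured about 8 weeks before it.

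Finally, more tests at N = 30 buy limited information. If the true correlation is near the 0.25 that VII.1 cites, the interval will probably include zero. That supports an exploratory label, not leaving the comparison out.

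None of these arguments reaches VII.4. Its window matches neither scan implied by endpoint 2, and its detectable difference does not follow from its own group sizes.

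**Conclusion.** The point holds in two parts of different weight.

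- **Pairing.** The follow-up scan with the longest lead over end PSA, about 8 weeks (56 to 60 days), is not compared with it. Section III is consistent with aim 2 as it stands. Adding the comparison is a low-cost way to serve the early-biomarker question in Section I.c.
- **Power statement.** VII.4 should be corrected. It claims detectability for a change at three months of ADT that no scheduled scan captures. For 8 versus 22 patients the 80%-power difference is about 1.20 SD, not 0.51, and power at 0.51 SD is about 22%.

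The lead times rest on the sample schedule and hold in order under the variations tried. The power figures assume two-sided 0.05, a common SD and the plan's own 8 expected failures. The documents do not show how far the SD differs once EBRT has begun, so the direction of that error is open. VII.2 cites a week-6 tumor change of −0.29 whose sign convention is unclear beside the increase described in Section I.c.

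**What to change.** Changes to wording in Sections III and VII.4:

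1. **Endpoint 2, correlations.** Keep TP2 and TP3 versus end PSA as named. Add mpMR parameters at the 8-week ADT scan, and their change from baseline, versus end PSA as a labelled exploratory correlation with a 95% CI. Call it the 8-week ADT scan, because the sample schedule numbers it differently from the text.
2. **Endpoint 2, split.** State that the >0.5 versus ≤0.5 comparison uses TP2 and TP3, with TP1 added as exploratory. Note that TP3 comes after the PSA that defines the groups, so it describes response and cannot predict it.
3. **VII.4.** Restate it for the scheduled scans used in that comparison. Say that the SD is borrowed from a 3-month window of ADT alone. Replace 0.51 SD with the two-group value, about 1.20 SD for 8 versus 22 at two-sided 0.05, and state the alpha.

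No scan, blood draw or patient is added, and the TP2 and TP3 analyses keep their present power because nothing is placed ahead of them. The cost is more unadjusted tests. Per parameter, the chance of at least one false positive rises from about 10% to 14% counting correlations alone. It is about 23% if five tests are counted, and 26% for all six correlations and splits, against 18% for the four already implied. Analysing TP1 both as a level and as a change adds to this, so the report should give the number of tests run.
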